# 16.2.1.5. CHANGE IN MEAN SITTING DBP AND SBP BETWEEN VISIT 4 (WEEK 8) AND VISIT 5 (WEEK 12)

Change in sitting SBP and DBP between patients under extemporaneous combination of NEB/RAM 5/5 mg versus patients uptitrated to the extemporaneous combination of NEB/RAM 5/10 mg will be compared using independent samples t-test. The secondary endpoint will be presented in a descriptive manner using n, mean, median, SD, Q1, Q3, and minimum and maximum. Assumption of normality will be investigated using Wilk-Shapiro test. If the data is found to be non-Normal, the independent samples t-test will be replaced by Wilcoxon rank-sum test.

16.2.1.6. Number and proportion of patients achieving the BP goal (sitting BP < 140/90 mmHg) will be summarized for Visit 2 (Week 0), Visit 3 (Week 4), Visit 4 (Week 8) and Visit 5 (Week 12) along with percentage and 95% CI (Clopper Pearson). A p-value using McNemar's test, or exact McNemar's test proposed when one of the cell frequency is 0, will be presented to compare the proportion of patients achieving the Standard BP goal (sitting BP < 140/90 mmHg) between Visit 2 and Visit 3, Visit 2 and Visit 4, Visit 2 and Visit 5, and, as well as, between Visit 3, Visit 4 and Visit 5.

Page 31 of 46

16.2.1.7. Number and proportion of patients achieving the optimal BP goal(sitting BP < 130/80 mmHg in patients < 65 years old/sitting BP < 140/80 mmHg in patients  $\geq 65$  years old)

The number of patients achieving the BP goal (sitting BP < 130/80 mmHg in patients < 65 years old/sitting BP < 140/80 mmHg in patients  $\geq$  65 years old) will be summarized for Visit 2 (Week 0), Visit 3 (Week 4), Visit 4 (Week 8) and Visit 5 (Week 12) along with percentage and 95% CI (Clopper Pearson). A p-value using exact McNemar's test will be presented to compare the proportion of patients achieving the BP goal (sitting BP < 130/80 mmHg in patients < 65 years old/sitting BP < 140/80 mmHg in patients  $\geq$  65 years old) between Visit 2 and Visit 3, as well as Visit 2 and Visit 4 as well as Visit 2 and Visit 5. A p-value using McNemar's test will be presented to compare the proportion of patients achieving the BP goal (sitting BP < 130/80 mmHg) between Visit 3, Visit 4 and Visit 5.

## 16.3. Exploratory Efficacy

## 16.3.1. Exploratory Efficacy Variables & Derivations

Change in mean sitting DBP and SBP between Visit 1 (Week -4) and Visit 2 (Week 0), Visit 3 (Week 4), Visit 4 (Week 8) and Visit 5 (Week 12):

- In the group of patients who were on NEB 5 mg and RAM 5 mg at Visit 1 (Week -4) and continued to be on the same therapies.
- In the group of patients who switched to NEB 5 mg or RAM 5 mg from any other BBs or ACEs at Visit 1 (Week -4).

To assess change in mean sitting DBP and SBP, for uncontrolled patients at Visit 3 (Week 4), between Visit 2 (Week 0) and Visit 3 (Week 4).

To assess change in mean sitting DBP and SBP, for uncontrolled patients at Visit 4 (Week 8), between Visit 2 (Week 0) and Visit 4 (Week 8) and between Visit 3 (Week 4) and Visit 4 (Week 8).

Number and proportion of patients achieving the standard BP goal (sitting SBP/DBP < 140/90 mmHg) at Visit 2 (Week 0), Visit 3 (Week 4), Visit 4 (Week 8) and Visit 5 (Week 12): In the group of patients who were on NEB 5 mg and RAM 5 mg at Visit 1 (Week -4) and continued to be on the same therapies.

In the group of patients who switched to NEB 5 mg or RAM 5 mg from any other BBs or ACEs at Visit 1 (Week 4).

Number and proportion of patients the optimal BP goal (sitting BP < 130/80 mmHg in patients <65 years old/sitting BP < 140/80 mmHg in patients  $\geq$  65 years old) at Visit 2 (Week 0), Visit 3 (Week 4), Visit 4 (Week 8) and Visit 5 (Week 12):

In the group of patients who were on NEB 5 mg and RAM 5 mg at Visit 1 (Week -4) and continued to be on the same therapies.

In the group of patients who switched to NEB 5 mg or RAM 5 mg from any other BBs or ACEs at Visit 1 (Week 4).

Page 32 of 46

Number and proportion of patients divided into subgroups according to the hypertension grade, CHD, the presence of diabetes and/or of hypercholesterolemia achieving the standard BP goal (sitting SBP/DBP < 140/90 mmHg) at Visit 2 (Week 0), Visit 3 (Week 4), Visit 4 (Week 8) and Visit 5 (Week 12).

In the group of patients who were on NEB 5 mg and RAM 5 mg at Visit 1 (Week -4) and continued to be on the same therapies.

In the group of patients, who switched to NEB 5 mg or RAM 5 mg from any other BBs or ACEs at Visit 1.

Number and proportion of patients divided into subgroups according to the hypertension grade, CHD, the presence of diabetes and/or of hypercholesterolemia achieving the optimal BP goal (sitting BP < 130/80 mmHg in patients < 65 years old/sitting BP < 140/80 mmHg in patients ≥ 65 years old) at Visit 2 (Week 0), Visit 3 (Week 4), Visit 4 (Week 8) and Visit 5 (Week 12). In the group of patients who were on NEB 5 mg and RAM 5 mg at Visit 1 (Week -4) and continued to be on the same therapies.

In the group of patients, who switched to NEB 5 mg or RAM 5 mg from any other BBs or ACEs at Visit 1.

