4 TRIAL OBJECTIVES AND ENDPOINTS

Note: For the purpose of this study, uncontrolled BP is defined as sitting SBP/DBP:

- \geq 130/80 mmHg in patients < 65 years old
 - $\geq 140/80$ mmHg in patients ≥ 65 years old

OBJECTIVES	ENDPOINTS	JUSTIFICATION FOR ENDPOINTS
Primary		
 To assess the antihypertensive efficacy of the extemporaneous combination of NEB 5 mg with RAM 2.5 mg, RAM 5 mg or RAM 10 mg in lowering sitting Systolic blood pressure (SBP) between Visit 2 (Week 0) and Visit 5 (Week 12) in patients with uncontrolled blood pressure (BP) previously treated with NEB 5 mg or RAM 5 mg monotherapies for at least 30 days. 	• Change in mean sitting SBP between Visit 2 (Week 0) and Visit 5 (Week 12).	• The association between elevated SBP and increased mortality risk has been reported in literature in individuals over age 50. ¹⁶
Secondary		
• To assess the antihypertensive efficacy of the extemporaneous combination of NEB 5 mg with RAM 2.5 mg, RAM 5 mg or RAM 10 mg in lowering sitting Diastolic BP (DBP) between Visit 2 (Week 0) and Visit 5 (Week 12) in patients with uncontrolled BP previously treated with NEB 5 mg or RAM 5 mg monotherapies for at least 30 days.	• Change in mean sitting DBP between Visit 2 (Week 0) and Visit 5 (Week 12).	• The association between elevated DBP and increased mortality rate has been reported in literature especially in younger patients. ¹⁶

RENARIN	Global Medical Department		
	Protocol Template		
Identification Number	Version Number	State	Effective date
FORM-000050125	3.0, CURRENT	Effective	13 May, 2022

OBJECTIVES	ENDPOINTS	JUSTIFICATION FOR ENDPOINTS
 To assess the antihypertensive efficacy of the extemporaneous combination of NEB 5 mg with RAM 2.5/5/10 mg in lowering sitting DBP and SBP between: Visit 2 (Week 0) and Visit 3 (Week 4) Visit 2 (Week 0) and Visit 4 (Week 8) 	 Change in mean sitting DBP and SBP between: Visit 2 (Week 0) and Visit 3 (Week 4) Visit 2 (Week 0) and Visit 4 (Week 8) 	• For individuals over 50, the mortality rate began to significantly increase at a SBP \geq 140 independent of DBP. In individuals \leq 50 years of age, DBP was the more important predictor of mortality. ¹⁶

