 To assess the antihypertensive efficacy in terms of sitting DBP and SBP between Visit 1 (Week -4) and Visit 2 (Week 0), Visit 3 (Week 4), Visit 4 (Week 8), and Visit 5 (Week 12) in the overall population. 	• Change in mean sitting DBP and SBP between Visit 1 (Week -4) and Visit 2 (Week 0), Visit 3 (Week 4), Visit 4 (Week 8), and Visit 5 (Week 12) in the overall population.	To gain specific knowledge on the antihypertensive effect of the extemporaneous combination in patients uncontrolled after 30 days of combined therapy.
 To evaluate sitting DBP and SBP between Visit 1 (Week -4) and Visit 2 (Week 0), Visit 3 (Week 4), Visit 4 (Week 8) and Visit 5 (Week 12) in patients who were on NEB 5 mg and RAM 5 mg at Visit 1 and continued to be on the same therapies or who switched to NEB 5 mg or RAM 5 mg from any other beta blocker (BB) or angiotensin-converting enzyme inhibitors (ACE- is) at Visit 1. 	 Change in mean sitting DBP and SBP between Visit 1 (Week -4) and Visit 2 (Week 0), Visit 3 (Week 4), Visit 4 (Week 8), and Visit 5 (Week 12) in the following subgroups: in the group of patients who were on NEB 5 mg and RAM 5 mg at Visit 1 and continued to be on the same therapies. in the group of patients who switched to NEB 5 mg or RAM 5 mg from any other BB or ACE- i at Visit 1. 	Evaluation of the antihypertensive efficacy of combination therapy in the subgroup of patients who were on nebivolol or on ramipril at the inclusion in the study or who switched from a different BB or ACE-i will provide useful information on the impact (if any) that previous monotherapies have on the antihypertensive effect of the extemporaneous combination.
• To evaluate sitting DBP and SBP at Visit 3 (Week 4), Visit 4 (Week 8), and Visit 5 (Week 12) in patients with uncontrolled hypertension.	• Mean sitting DBP and SBP for uncontrolled patients at Visit 3 (Week 4), Visit 4 (Week 8), and Visit 5 (Week 12).	To gain specific knowledge on the antihypertensive effect of the extemporaneous combination in patients uncontrolled after 30 days of combined therapy.

MENARINI	Global Medical Department		
	Protocol Template		
Identification Number	Version Number State Effective date		
FORM-000050125	3.0, CURRENT	Effective	13 May, 2022

OBJECTIVES	ENDPOINTS	JUSTIFICATION FOR ENDPOINTS

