5 STUDY DESIGN

This is a Phase IV, interventional, multicenter, open-label, multinational study with 2 study periods (a Run-in period of 4 weeks and an Assessment period of 12 weeks) to assess the efficacy and safety of the extemporaneous combination of NEB and RAM in reducing SBP and DBP in hypertensive patients uncontrolled by monotherapy.

The trial will be conducted in approximately 26 investigational clinical sites in Bulgaria, Poland, and Hungary. The total study duration is 16 weeks including a Run-in period of 4 weeks and an Assessment period of 12 weeks.

Note: For the purpose of this study, uncontrolled BP is defined as sitting SBP/DBP:

- \geq 130/80 mmHg in patients < 65 years old
 - \geq 140/80 mmHg in patients \geq 65 years old

Screening Visit 1 (Week -4):

Hypertensive patients with SBP ranging from ≥ 140 to ≤ 179 mmHg and/or DBP ranging from ≥ 90 to ≤ 109 mmHg on treatment, for at least 30 days prior to screening, with NEB 5 mg or any other BB, or RAM 5 mg or any other ACE-i will be screened for eligibility (Visit 1). Patients that did not meet eligibility criteria will be considered as screening failures and will not be re-screened.

Run-in period from Visit 1 (Week -4) to Visit 2 (Week 0):

On the same day of the Screening Visit, eligible patients will enter a Run-in period, during which:

- Patients receiving NEB 5 mg or RAM 5 mg will continue the same therapy for 4 weeks.
- Patients on any other BB will be assigned to monotherapy with NEB 5 mg while patients on any other ACE-i will be assigned to monotherapy with RAM 5 mg for 4 weeks.

The study is designed in order to ensure that 1:1 ratio between patients in the NEB and RAM arms will be achieved. For details see Section 5.

Assessment period from Visit 2 (Week 0) to Visit 5 (Week 12):

After 4 weeks (\pm 2 days) of the Run-in period of monotherapy (Week 0), BP will be further assessed at Visit 2.

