6.2 Inclusion and Exclusion Criteria

6.2.1 Inclusion Criteria

Patient will be considered eligible to be enrolled in the study only if he/she meets all the following inclusion criteria:

- 1. Willing to comply with all study activities and procedures for the duration of the study and provided signed, written informed consent prior to any study procedures at Screening Visit.
- 2. Male or female patients aged ≥ 18 years with hypertension with mean sitting SBP ≥ 140 mmHg and ≤ 179 mmHg and/or mean sitting DBP ≥ 90 mmHg and ≤ 109 mmHg at Visit 1 (screening), while on monotherapy treatment either with BBs (NEB 5 mg or any dose if other BB) or ACE-is (RAM 5 mg or any dose if other ACE-i) for at least 30 days before Visit 1 (screening) and, as per Investigator's judgement, is deemed appropriate for a combination treatment with BB and ACE-i.
- 3. Ability to take oral medication and willing to adhere to the drug regimen.

RENARIN	Glol	oal Medical Department	
	Protocol Template		
Identification Number	Version Number	State	Effective date
FORM-000050125	3.0, CURRENT	Effective	13 May, 2022

- 4. Female patient of childbearing potential is eligible to participate if she is not pregnant, or not breastfeeding. A woman is considered fertile following menarche and until becoming postmenopausal unless permanently sterile. Women of childbearing potential must agree to use of highly effective contraception (e.g., method of birth control throughout the study period and for 4 weeks after study completion defined as a method which results in a failure rate of less than 1% per year) and also must refrain from donating or storing eggs during this time. Highly effective contraception methods can be:
 - Combined hormonal contraception (estrogen- and progestogen-containing) associated with inhibition of ovulation (oral, intravaginal, and transdermal).
 - Progestogen-only hormonal contraception associated with inhibition of ovulation (oral, injectable, and implantable).
 - Intrauterine device.
 - Intrauterine hormone-releasing system.
 - Bilateral tubal occlusion.
 - Vasectomized partner (procedure conducted at least 2 months before the screening), (provided that partner is the sole sexual partner of the trial participant and that the vasectomized partner has received medical assessment of the surgical success).

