## 16.3.2. Analysis of Exploratory Efficacy Variables

Exploratory efficacy variables will be summarized in a descriptive manner using ENR and mITT populations for Visits 1, 2, 3, 4 and 5.

Change in sitting DBP and SBP from Visit 1 (Week -4) will be using paired t-test. The p-value obtained from the paired t-test will be presented for the visits - Visit 2 (Week 0), Visit 3 (Week 4), Visit 4 (Week 8) and Visit 5 (Week 12). Assumption of Normality will be investigated using Wilk-Shapiro test. If the data is found to be non-Normal, then paired t-test will be replaced by Wilcoxon signed rank test. A descriptive summary using n, mean, median, SD, Q1, Q3, minimum, and maximum is also presented.

Change in mean sitting DBP and SBP for uncontrolled patients between Visit 2 (Week 0) and Visit 3 (Week 4) will be using paired t-test. The p-value obtained from the paired t-test along with n, mean, median, SD, Q1, Q3, minimum, and maximum will be presented. Assumption of Normality will be investigated using Wilk-Shapiro test. If the data is found to be non-Normal, then paired t-test will be replaced by Wilcoxon signed rank test.

The number of patients achieving standard BP goal (sitting BP < 140/90 mmHg) will besummarized for Visits 2, 3, 4 and 5, along with percentage and 95% CI for the proportion. A p-value using exact McNemar's test will be presented to compare the proportion of patients achieving the standard BP goal (sitting BP < 140/90 mmHg) between Visit 2 and Visit 3 as well as Visit 2 and Visit 4 and as well as Visit 2 and Visit 5. A p-value using McNemar's test will be presented to compare the proportion of patients achieving the BP goal (sitting BP < 140/90 mmHg) between Visit 3 and Visit 4. A two-sided p-value using McNemar's test between Visit 3 vs. Visit 5 and between Visit 4 vs. Visit 5.

Page 33 of 46

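### Blood-pressure changes for continued and switched patients start at Visit 1, so they mix the run-in switch with the combination effect that the subgroups are meant to show

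*SAP*

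**What the plan says.** Protocol section 6.2.1 admits patients on NEB 5 mg or RAM 5 mg, and patients on another beta blocker or ACE inhibitor at any dose (for beta blockers, "any dose if other BB"). At Visit 1 the first group continues and the second is switched to a fixed dose. Protocol section 5 puts it for beta blockers as "Patients on any other BB will be assigned to monotherapy with NEB 5 mg"; patients on another ACE inhibitor go to RAM 5 mg. Protocol section 5.1 places the dose at the end of the visit, so the Visit 1 reading precedes the switch. The combination starts at Visit 2.

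Protocol section 4 gives the reason for splitting patients into continued and switched: the split will "provide useful information on the impact (if any) that previous monotherapies have on the antihypertensive effect of the extemporaneous combination".

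The variable attached to that purpose in SAP 16.3.1 opens "Change in mean sitting DBP and SBP between Visit 1 (Week -4) and Visit 2 (Week 0" and runs on to Visits 3, 4 and 5. The protocol endpoint has the same starting point. SAP 16.3.2 gives the test, "Change in sitting DBP and SBP from Visit 1 (Week -4) will be using paired t-test", and the populations: "Exploratory efficacy variables will be summarized in a descriptive manner using ENR and mITT populations for Visits 1, 2, 3, 4 and 5".

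SAP 6.2 sets the Visit 2 measurement as baseline for analyses of combination therapy. The Visit 2 to Visit 5 SBP change is planned for the whole mITT (SAP 16.1.3), the per-protocol set (16.1.5) and the mITT including all patients (16.4). Prior therapy does not split any of these. It is not a covariate in the MMRM (16.1.4), nor among the subgroups in SAP 7.5.

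The primary objective (protocol section 4) describes patients "previously treated with NEB 5 mg or RAM 5 mg monotherapies for at least 30 days".

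**The concern.** The question is about the combination, whose effect is the change after Visit 2. The planned variable starts four weeks earlier, at a reading taken on a different drug for every switched patient. It adds whatever the switch did to whatever the combination did. The switch could move pressure either way, because any previous dose is replaced by a fixed 5 mg.

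A reader who sees a larger or smaller Visit 1 to Visit 5 fall in switched patients would naturally credit or blame the combination. The table cannot support that. The quantity that could, the change from Visit 2 with its own interval, is not listed for either group.

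**Working it through.** **Planning figures.** The point does not rest on the sample size, but it borrows the SD, so that is checked first. Protocol section 12.2: difference 2.4, SD 12.0, one-sided alpha 0.05, power 90%. n = ((1.645 + 1.282) × 12 / 2.4)² = 214.1, so 215, as stated. The planning mean is 5.4 mmHg.

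**1. What the planned variable measures.** For each patient:

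(Visit 1 to Visit 5) = (Visit 1 to Visit 2) + (Visit 2 to Visit 5) = run-in change + combination change.

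Suppose both groups have the same combination change of −5.4 mmHg and the switch alone adds s to the run-in change of switched patients. The documents give no s; the values below are assumed, with zero included. Any run-in change common to both groups is left out, since it cancels.

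| s (mmHg) | Continued, V1 to V5 | Switched, V1 to V5 | Difference | True difference in combination effect |
|---|---|---|---|---|
| −5 | −5.4 | −10.4 | −5 | 0 |
| −3 | −5.4 | −8.4 | −3 | 0 |
| 0 | −5.4 | −5.4 | 0 | 0 |
| +3 | −5.4 | −2.4 | +3 | 0 |
| +5 | −5.4 | −0.4 | +5 | 0 |

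The false difference equals s. At 3 to 5 mmHg it is 3/5.4 = 56% to 5/5.4 = 93% of the planning mean.

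**2. Can the Visit 2-based change be recovered?**

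*In the mITT, the mean can.* Every mITT patient has Week 0 and Week 12 values (SAP 5.2), and Visit 1 pressure is needed for eligibility. The group mean for Visit 1 to Visit 5 minus that for Visit 1 to Visit 2 is the group mean for Visit 2 to Visit 5.

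*Its precision cannot.* SD = √(a² + b² − 2rab), where a and b are the SDs of the two Visit 1-based changes and r is their correlation, which no planned output reports. With a = b = 12 (assumed equal to the protocol's SD), the SD is 17.0 at r = 0, 12.0 at r = 0.5 and 5.4 at r = 0.9.

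*In the Enrolled set, not even the mean.* Patients found controlled, intolerant or non-adherent at Visit 2 leave the study (protocol section 5), so they contribute to Visit 1 to Visit 2 only. As an illustration, assume usual SBP 145, between-patient SD 12, within-patient SD 6, 8 or 10, no drug effect, Visit 1 SBP 140 to 179 and staying in if Visit 2 SBP is at least 130. The simulated mean Visit 1 to Visit 2 change is −1.50, −2.48 or −3.58 in all enrolled, against −1.22, −1.71 or −2.04 in those who stay. Subtraction would be off by 0.28, 0.77 or 1.54 mmHg from withdrawal alone.

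**3. Prior exposure at Visit 2.** The run-in is 4 weeks ± 2 days, so 28 ± 2 = 26 to 30 days. Switched patients have had NEB 5 mg or RAM 5 mg for 26 to 30 days and reach 30 only at the end of the window. Continued patients have at least 30 + 26 = 56 days.

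**The case against.** These analyses are exploratory and summarised descriptively, and SAP 7.5 disclaims power within subgroups. The SAP plans within-group paired tests only, with no test of continued against switched, so the error of size s enters an informal comparison and not a planned inference. The Visit 1 to Visit 2 change is tabulated by group, so a careful reader sees the run-in shift beside the later changes and can subtract in the mITT. BP-goal rates at Visits 2 to 5 are also planned by group. The table shells cited in SAP section 4 are not among the documents, so an unlisted table cannot be excluded.

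All of this stands, and it limits the point. It does not remove it. Subtraction gives a mean with no interval, and goal rates depend on where pressure stood at Visit 2 and do not give an effect in mmHg.

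Three stronger readings are tempting and are not supported:

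- *The primary result is biased by the switch.* The run-in puts every patient on NEB 5 mg or RAM 5 mg before the Visit 2 baseline. Bias would need a switch effect still drifting after four weeks, and the documents give no evidence of that.
- *Regression to the mean explains a difference between the groups.* Both groups enter on the same Visit 1 criterion. A fall from that reading is expected in both, so it does not by itself create a contrast between them.
- *Switched patients fall outside the objective, so its wording or the run-in is wrong.* The gap is 0 to 4 days and has no shown numerical effect. It is a conflict of wording, and the documents do not say which text should give way.

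**Conclusion.** The planned blood-pressure changes for continued and switched patients do not answer the question that the protocol sets for those groups, and they depart from the SAP's own rule on the combination baseline. Any switch effect appears in full as a between-group difference in the Visit 1 to Visit 5 change. Its size is unknown; the 3 to 5 mmHg used here is an assumption and zero is possible. What is missing is the Visit 2-based change by prior therapy as a listed analysis with its own SD and interval. In the mITT the mean alone is recoverable; in the Enrolled set it is not.

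The primary endpoint, test and population are untouched. This is a worthwhile, inexpensive improvement to an exploratory analysis. The 30-day wording is a separate inconsistency to be reconciled.

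**What to change.** In SAP 16.3, for the mITT, add the change in SBP and DBP from Visit 2 to Visits 3, 4 and 5 (n, mean, SD, 95% CI) for continued and for switched patients. Name the Visit 2 to Visit 5 SBP change in continued patients as a supplementary result. Use the Visit 1 to Visit 2 change only to describe the run-in and switch. Define the split by the protocol's terms; the baseline category in SAP section 10 labels the second group as other BBs or CCBs, whereas the protocol has other BB or ACE-i.

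Separately, the sponsor should reconcile the primary objective's 30-day prior treatment with the 4-week ± 2-day run-in.

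Cost: SAP wording and a few table rows; all data are already collected. The subgroup intervals will be wider. At SD 12 the 95% half-width is about 1.6 mmHg for all 215 (1.97 × 12/√215). It is about 3.3, 2.3 or 1.9 mmHg if a group makes up 25%, 50% or 75% of them. The share is assumed, as the documents do not give it.

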- Number and proportion of patients achieving the standard BP goal (sitting SBP/DBP < 140/90 mmHg) and the optimal BP goal (sitting BP < 130/80 mmHg in patients < 65 years old/sitting BP < 140/80 mmHg in patients ≥ 65 years old) at Visit 2 (Week 0), Visit 3 (Week 4), and Visit 4 (Week 8).
- Change in mean sitting DBP and SBP from Visit 1 (Week -4) to Visit 2 (Week 0), Visit 3 (Week 4), Visit 4 (Week 8), and Visit 5 (Week 12) in the overall population.
- Change in mean sitting DBP and SBP from Visit 1 (Week -4) to Visit 2 (Week 0), Visit 3 (Week 4), Visit 4 (Week 8), and Visit 5 (Week 12) in the overall population:
 - in the group of patients who were on NEB 5 mg and RAM 5 mg at Visit 1 and continued to be on the same therapies.
 - in the group of patients who switched to NEB 5 mg or RAM 5 mg from any other BBs or ACE-is at Visit 1.
- Mean sitting DBP and SBP for uncontrolled patients at Visit 3 (Week 4), at Visit 4 (Week 8), and at Visit 5 (Week 12).
- Change in mean sitting DBP and SBP for uncontrolled patients from Visit 2 (Week 0) to Visit 3 (Week 4); from Visit 3 (Week 4) to Visit 4 (Week 8); from Visit 4 (Week 8) to Visit 5 (Week 12).
- Number and percentage (proportion) of patients achieving the standard BP goal (sitting SBP/DBP < 140/90 mmHg) and the optimal BP goal (sitting BP < 130/80 mmHg in patients < 65 years old/sitting BP < 140/80 mmHg in patients ≥ 65 years old) at Visit 2 (Week 0), Visit 3 (Week 4), Visit 4 (Week 8), and Visit 5 (Week 12):
 - in the group of patients who were on NEB 5 mg and RAM 5 mg at Visit 1 (Week -4) and continued to be on the same therapies.
 - in the group of patients who switched to NEB 5 mg or RAM 5 mg from any other BBs or ACE-is at Visit 1 (Week -4).
- Number and percentage (proportion) of patients achieving the standard BP goal (sitting SBP/DBP < 140/90 mmHg) and the optimal BP goal (sitting BP < 130/80 mmHg in patients < 65 years old/sitting BP < 140/80 mmHg in patients ≥ 65 years old) who were on NEB 5 mg and RAM 5 mg at Visit 1 and continued to be on the same therapies by their hypertension grade, CHD, presence of diabetes, and/or of hypercholesterolemia, at Visit 2, Visit 3, Visit 4, and Visit 5.

MENARING	Global Medical Department		
		Protocol Template	
Identification Number	Version Number	State	Effective date
FORM-000050125	3.0, CURRENT	Effective	13 May, 2022

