To evaluate sitting DBP and SBP at Visit 3 (Week 4), Visit 4 (Week 8), and Visit 5 (Week 12) in patients with uncontrolled hypertension.  To assess the change in sitting DBP and SBP from Visit 2 (Week 0) to Visit 3 (Week 4), from Visit 3 (Week 4) to Visit 4 (Week 8), and from Visit 4 (Week 8) to Visit 5 (Week 12) in patients with uncontrolled hypertension.	Mean sitting DBP and SBP for uncontrolled patients at Visit 3 (Week 4), Visit 4 (Week 8), and Visit 5 (Week 12).  Change in mean sitting DBP and SBP for uncontrolled patients from Visit 2 (Week 0) to Visit 3 (Week 4); from Visit 3 (Week 4) to Visit 4 (Week 8); and from Visit 4 (Week 8) to Visit 5 (Week 12).

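### SAP 16.3 measures change in uncontrolled patients only over intervals ending at the visit that defines them, and omits the listed Visit 4 to Visit 5 change

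*SAP*

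**What the plan says.** Protocol section 4 lists, as an exploratory endpoint, the change in sitting DBP and SBP in uncontrolled patients over three successive intervals: Visit 2 to 3, Visit 3 to 4 and Visit 4 to 5. SAP 2.3 repeats it, including "from Visit 4 (Week 8) to Visit 5 (Week 12) in patients with uncontrolled hypertension", and protocol 12.5 also includes "from Visit 4 (Week 8) to Visit 5 (Week 12". None of these places says at which visit a patient must be uncontrolled.

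SAP 16.3.1 does say. The first derivation is the change "for uncontrolled patients at Visit 3 (Week 4), between Visit 2 (Week 0) and Visit 3 (Week 4". The second is the change "for uncontrolled patients at Visit 4 (Week 8), between Visit 2 (Week 0) and Visit 4 (Week 8) and between Visit 3 (Week 4"; the last of these intervals likewise ends at Visit 4. No derivation for uncontrolled patients runs from Visit 4 to Visit 5.

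SAP 16.3.2 states a test for uncontrolled patients over one interval only: "Change in mean sitting DBP and SBP for uncontrolled patients between Visit 2 (Week 0) and Visit 3 (Week 4) will be" tested by paired t-test, with the signed rank test if normality fails. It does not name the classifying visit. SAP 3.3, which summarises changes from the planned analysis, does not mention the missing interval.

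**The concern.** When the last reading of an interval also decides who is counted, the group is selected on the outcome. A patient whose pressure fell below the limit at Visit 3 cannot appear in the Visit 2 to 3 result for patients uncontrolled at Visit 3. Those who remain include patients whose Visit 3 reading happened to be high. Their mean fall is pulled towards zero even if every patient has the same true response.

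The missing interval is a separate matter. Visit 4 to 5 is the only interval in which NEB/RAM 5/10 mg is given, and it is listed in three places. As written, the exploratory tables would contain a biased look backwards and lack one of the listed changes.

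**Working it through.** **1. The passages side by side**

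| Interval | Listed (protocol 4 and 12.5, SAP 2.3) | SAP 16.3.1 group | Test for uncontrolled patients in SAP 16.3.2 | Nearest secondary analysis |
|---|---|---|---|---|
| Visit 2–3 | yes | uncontrolled at Visit 3 (end) | paired t-test | 16.2.1.1, all patients |
| Visit 2–4 | no | uncontrolled at Visit 4 (end) | none stated | 16.2.1.2, all patients |
| Visit 3–4 | yes | uncontrolled at Visit 4 (end) | none stated | 16.2.1.4, 5/2.5 versus stepped up to 5/5 |
| Visit 4–5 | yes | absent | absent | 16.2.1.5, 5/5 versus stepped up to 5/10 |

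SAP 6.6 gives a formula for the Visit 4 to 5 change but no analysis in uncontrolled patients.

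**2. Inputs**

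The documents give no figure for this analysis. The only usable ones are in protocol 12.2: a mean SBP fall of 5.4 mmHg and an SD of 12.0 mmHg. The sample size reproduces with 12.0 as the SD of the within-patient change: n = ((1.645 + 1.282) × 12 / 2.4)² = 214.1, rounded up to 215. All other inputs below are assumptions. The documents write the limits as pairs (130/80 under 65 years, 140/80 from 65) without saying whether one raised component suffices, so both rules were tried.

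**3. Simulation anchored on protocol 12.2**

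The model is: reading = patient's true level − effect + visit noise, so that SD of change² = 2 × (noise SD)² + (effect SD)² = 144. With equal effects the noise SD is 12/√2 = 8.5. Assumed: Visit 2 mean 140 to 152, between-patient SD 6 to 14, 40% aged 65 or over, a flat 5.4 fall at every visit after Visit 2, no titration.

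- SBP-only rule, equal true response: Visit 2–3 in patients uncontrolled at Visit 3 shows a fall of 3.4 to 4.6. The shortfall is 5.4 − 4.6 = 0.8 to 5.4 − 3.4 = 2.0. If the effect varies between patients (SD 6) the displayed fall can be as low as 2.1, but part of that is genuinely poorer response.
- SBP-only rule, Visit 3–4, true change 0: patients uncontrolled at Visit 4 show an apparent rise of 1.0 to 4.1. Patients uncontrolled at Visit 3 show an apparent fall of the same size.
- SBP-or-DBP rule (one scenario, DBP mean 88): Visit 2–3 shows 5.0, a shortfall of 0.4. Visit 3–4 shows +0.7 when grouped at the end and −0.7 when grouped at the start.

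**4. Simulation with titration, SBP-or-DBP rule**

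Assumed: means 140–148/86–88, between-patient SD 13/8, visit SD 6–8.5/4–5.5, 35% aged 65 or over, protocol entry limits, effect −8/−5, step-up effect −3/−2, SBP–DBP correlation 0 or 0.5.

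- Visit 2–3, uncontrolled at Visit 3: true fall 8, understated by about 0.2 to 0.9.
- Visit 3–4, uncontrolled at Visit 4: the correct comparator is 3 × the proportion of the group stepped up at Visit 3, because the rest had no step-up. Against that, the fall is understated by about 0.5 to 1.7.
- Start-defined changes: the fall is overstated by about 0.3 to 1.6.
- Visit 2-based changes whose end visit did not define the group (for example Visit 2–4 in patients uncontrolled at Visit 3): within about 0.05 to 0.35 of the truth.

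The sizes are for SBP; the DBP bias was not sized.

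**The case against.** Much of the forward-looking information is already in the secondary analyses. Everyone entering the Assessment period is uncontrolled at Visit 2, so Visit 2 to 3 classified at its start is SAP 16.2.1.1. By protocol, the patients stepped up at Visit 3 are those uncontrolled at Visit 3, and 16.2.1.4 reports their Visit 3 to 4 change. Patients reach 5/10 only if uncontrolled at Visit 4 on 5/5, and 16.2.1.5 reports their Visit 4 to 5 change. All of this stands. What remains uncovered is a pooled Visit 4 to 5 result for patients uncontrolled at Visit 4, and those among them who move from 5/2.5 to 5/5, whom 16.2.1.5 does not isolate.

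The remedy also has a bias. Grouping at the start of the interval overstates the fall by a similar amount, in the flattering direction. With no true effect at all, selection at entry and at Visit 3 cancel, so the planned Visit 2 to 3 change is about zero. This also stands. It is the reason to show the Visit 2-based changes alongside and to withhold p-values from both selected sets.

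A reader might infer that the phrase "patients uncontrolled after 30 days of combined therapy" is the purpose of this change endpoint, so that the SAP contradicts its own aim. In protocol section 4 that phrase justifies two other exploratory endpoints: change from Visit 1, and mean BP in uncontrolled patients at Visits 3 to 5. The change endpoint carries a different justification, about patients who continued or switched therapy.

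The table shells were not available for this review and may add detail.

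**Conclusion.** Both parts hold. SAP 16.3.1 selects on the outcome in all three derivations for uncontrolled patients, and SAP 16.3 omits a listed interval without declaring it. The direction of the bias follows from the grouping rule. Its size rests on assumed variances and BP levels and on how SBP and DBP combine: about 0.2 to 0.9 mmHg (Visit 2–3) and 0.5 to 1.7 mmHg (Visit 3–4) if DBP alone can make a patient uncontrolled, and more under an SBP-only rule.

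Three stronger readings are not supported:

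- That the grouping creates most of an apparently weak response. The Visit 2–3 shortfall is under 1 mmHg of 8 under the SBP-or-DBP rule. Setting the Visit 3–4 result against a full 3 mmHg step-up is not like for like, because the group includes patients who were not stepped up.
- That all the selected changes are tested. SAP 16.3.2 states a test for uncontrolled patients only for Visit 2 to 3.
- That the SAP nowhere looks at what follows a step-up. SAP 16.2.1.4 and 16.2.1.5 do so in part.

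The analysis is exploratory and the primary result is unaffected. This is a minor-priority change.

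**What to change.** In SAP 16.3.1 and 16.3.2:

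- Define uncontrolled at the start of each listed interval: Visit 2 for Visit 2–3 (cross-refer to 16.2.1.1), Visit 3 for Visit 3–4, Visit 4 for Visit 4–5. This restores the Visit 4–5 change for all patients uncontrolled at Visit 4.
- Beside these, report Visit 2 to Visits 4 and 5 for patients uncontrolled at Visit 3, and Visit 2 to Visit 5 for patients uncontrolled at Visit 4. The end visits of these changes did not define the group.
- In these 16.3 tables, keep any change that starts or ends at the defining visit descriptive, without p-values, with a note on regression to the mean.
- State whether one raised component, SBP or DBP, is enough to classify a patient as uncontrolled for the analysis.
- Record the change in SAP 3.3, since protocol 12.5 foresees paired t-tests for exploratory changes between visits.

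The cost is SAP wording and the re-programming of a few exploratory tables. No new data are needed.
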